1 PROTOCOL SUMMARY

1.1 Synopsis

TITLE	A clinical trial to evaluate the effectiveness and safety of Dual Energy Cone-Beam Computed Tomography (DE-CBCT) imaging for assessment of jaw bone density
SPONSOR	Ray Co., Ltd.
DEVICE MANUFACTURER	Ray Co., Ltd.
RATIONALE	
Current radiologic imaging modalities used in dentistry provide information on the morphology of the hard tissues. Additional information on the density of bone has practical relevance, for example, in dental implant treatment planning, where local bone quality is a known strong predictor of successful implant osseointegration. The Dual-Energy Cone Beam Computed Tomography (DE-CBCT) device is designed to overcome limitations of traditional imaging and will provide assessment of jaw bone density in addition to morphological information.
 
This clinical trial will examine the application of DE-CBCT to assess jaw bone density and compare Hounsfield units (HU) values with multidetector CT, an established standard for assessing BD.

STUDY DESIGN	This is a single center, open-label trial, designed to enroll 24 patients. Both, the researcher and the subject know the treatment the participant is receiving.
PRIMARY OBJECTIVE	To evaluate the effectiveness and safety of DE-CBCT to evaluate jaw bone density and compare HU values with those of multidetector CT, an established standard for assessing BD.
NUMBER OF SUBJECTS	24 patients

SUBJECT SELECTION CRITERIA	
Inclusion Criteria:
 
 1. Patients who need x-ray imaging for dental treatment planning and/or diagnosis 2. Males or females aged older than 21 3. Can follow instructions to be positioned into the CT scanner 4. Can remain physically immobile during the CT scan acquisition 5. Voluntarily sign and date the informed consent 
Exclusion Criteria:
 
 1. Pregnancy 2. Patients who are unable to comprehend the risks of the study to provide informed consent 3. Extensive dental restorations, maxillofacial prosthesis, or orthopedic hardware that likely may cause artifacts and degrade quality, as determined by the study radiologists
TEST DEVICE, MODEL, PURPOSE	Dual Energy-Cone Beam Computed Tomography (DE-CBCT), RCT720
CONTROL DEVICE, MODEL, PURPOSE	Multidetector Computed Tomography (MDCT),
DURATION OF SUBJECT PARTICIPATION AND DURATION OF STUDY	
Subjects will be on study for up to 30 days
 
Total Study period: 12 months
 
Enrollment & Follow-up: 1 month
 
The total duration of the study is expected to 12 months. Once enrolled, the test subject will be on the study for one month including recruitment and final subject follow-up.

STUDY METHOD	
The study is based on two visits (VISIT 1 and VISIT 2)
 
 • DAY 0 (enrollment): Subject is queried for inclusion/exclusion criteria and informed about the study. If he/she agrees to participate, inclusion/exclusion criteria and informed consent will be documented. An imaging stent, which bears radiopaque markers, will be also created for each patient. • VISIT 1: Inclusion/exclusion criteria will be reconfirmed and the DE-CBCT imaging will be completed. • VISIT 2 (no more than 30 days since the enrollment): Inclusion/exclusion criteria will be reconfirmed and MDCT imaging completed. 
- Depending on availability of scheduling on MDCT unit, Visit 2 may occur on the same day as Visit 1.

Clinical Assessments	
The following assessments will be performed and recorded on Case Report Form:
 
 • Demographics • Any relevant medical history • Site-specific BD assessment (Region of Interest, ROI) • Adverse Events
PRIMARY ENDPOINT	Jaw BD (HU values) assessed by DE-CBCT and by MDCT
SECONDARY ENDPOINT	Agreement between the BD assessments by evaluators

SAFETY EVALUATIONS	Incidence of adverse events (AE): Adverse events on the days of the study visits will be documented. The PI/staff evaluates the severity of AE and the causal relationship using 'safety evaluation criteria.' The PI will report the case to the investigator/sponsor and IRB subsequently.
PLANNED INTERIM ANALYSES	None
STATISTICS Primary Analysis Plan	
 The correlation between DE-CBCT and MDCT HU values of bone density will be performed using Pearson. The agreement between DE-CBCT and MDCT HU values of bone density will be performed using Bland-Altman plots. In order to evaluate the observer reliability, Kappa statistics will be performed.
Rationale for Number of Subjects	
The correlation coefficient of human mandibular bone density (in HU) between CBCT and MDCT was observed to be 0.89, according to the study conducted by Parsa et al. (Reference paper: Bone quality evaluation at dental implant site using multidetector CT, micro-CT, and cone beam CT)
 
Using the formula below, the number of patients is calculated to be 7.
 $n = \left(\frac{z_{\alpha/2} + z_{\beta}}{C(r_0)} \right)^2 + 3, \quad C(r_0) = \frac{1}{2} \ln \left(\frac{1 + r_0}{1 - r_0} \right)$ 
Since we have three age groups (7x3 = 21) and expect the dropout rate to be 10% (21x(1+0.1)=24), a total of 24 patients will be enrolled for the current study.

1.2 Schema

Day 0	
PRE-STUDY SCREENING and RECRUITMENT	
 • Inform patients about the study • Identify and screen potential subjects for inclusion and exclusion criteria • Obtain informed consent • Fabricate stent for enrolled patients
Acceptable time frame: Day 1 to day 30	
VISIT 1	
 • Acquire dual energy CBCT scan of the jaws
Acceptable time frame: Day 1 to day 30	
VISIT 2*	
 • Acquire MDCT scan of the jaws

* Visit 2 shall not be more than 30 days before/after visit 1.

* Depending on availability of scheduling on MDCT unit, Visit 2 may occur on the same day as Visit 1.

1.3 Schedule of activities

Procedures	Screening	Study Visit 1	Study visit 2 (≤30 d from visit 1)
Allowable windows for visit	Day 0	Day 1	Day 30
Informed consent	X	X	
Demographics	X	X	
Medical history	X	X	
DE-CBCT		X	
MDCT			X

2 INTRODUCTION

2.1 Study Rationale

Current imaging modalities used in dentistry include 2-dimensional radiographs, and 3-dimensional CT imaging. All of these x-ray-based modalities provide information on the morphology and architecture of the dental hard tissues and alveolar bone. Although these images display relative degrees of solidity within these hard tissues, they are of limited value for reliable, qualitative assessment of the bone density. Information on the jaw bone density has practical relevance, for example, in dental implant treatment planning, where local bone quality is a known strong predictor of successful implant osseointegration.

The Dual-Energy Cone Beam Computed Tomography (DE-CBCT) device is designed to overcome limitations of traditional dental imaging and will provide assessment of jaw bone density in addition to morphological information. This clinical trial will examine the application of DE-CBCT to assess jaw bone density and compare this novel device with multidetector computed tomography (MDCT).

[figure not shown]
2.2 Background and Significance

Computed tomography (CT) is an x-ray-based imaging technique that produces cross-sectional images of the body. In all CT techniques, a collimated x-ray source and a detector revolve around the patient. The detector records photon attenuation by assessing the number of photons that exit the patient, registering this information at several hundred angles through the rotational arc. Complex mathematical algorithms translate this attenuation data into a three-dimensional (3D) map that spatially locates the attenuating structures.¹

MDCT is the most widely used CT scanner design across the world. In MDCT, multiple rows of detectors are incorporated into the array in the z-axis (craniocaudal axis, patient's head to foot), allowing capture of multiple image slices during each gantry revolution. Current detector spatial resolution allows imaging of submillimeter dimensions. Volumetric acquisition with isotropic imaging allows reformatting in planes different from the axial acquisition, without compromising image quality. Contemporary MDCT scanners have 64 to 128 rows of detectors, with some vendors manufacturing scanners with 320 and 640 detector rows.

CBCT is an advanced imaging modality with several applications in dentomaxillofacial diagnosis and treatment planning.²⁻⁸ In this technique, a cone-shaped x-ray beam and a detector rotate around the patient acquiring multiple projections that are reconstructed into a volumetric image. Depending on the manufacturer and protocol, detector pixel elements are in the range of 70 μ m to 400 μ m, providing high resolution 3D volumetric imaging.

In CT data, each voxel in the reconstructed CT volume is represented by a numerical gray value (CT number).¹ This number reflects the degree of x-ray attenuation and represents the average linear attenuation coefficient of that voxel. Major factors that influence the CT number include the tissue features (atomic number and density) and homogeneity and energy of the x-ray beam. CT numbers are expressed as Hounsfield units (HU), which expresses x-ray attenuation of a voxel relative to the

attenuation of water. In the HU scale, the CT number of water is defined as zero, and the CT number of air is defined as -1000. The HU values of ~ 200 and higher represent densities of trabecular and cortical bone.

CBCT and HU: Assessment of BD has relevance in dentistry. The degree of mineralization of bone at dental implant sites are strong determinants of implant osseointegration and stability. Likewise, closer representation of attenuation and CT numbers are important for third party applications of CT data that use automatic segmentation for computer-aided design and computer-aided manufacturing applications. Current dental CBCT units do not apply a standard scaling system for representing CT numbers, and attempts to convert CBCT numbers to HU are unsuccessful. In particular, the cone beam geometry of the x-ray beam produces scatter radiation and consequently decrease the signal-to-noise ratio, with a practical negative impact on contrast resolution of the CBCT image.¹

Studies from our group and others have shown that although the relationship between CBCT numbers and object density is linear, this relationship is influenced by several factors including imaging protocol and anatomic location.⁹⁻¹⁵ Collectively, these factors result in an inhomogeneity of CT numbers on CBCT scans. For example, the CT number of the same object differed depending on the anatomical location in which it was imaged.¹⁵ Specifically, the CT numbers of phantom objects were higher when placed within the anterior region of the jaw and lower in the posterior regions.^{9,15} Importantly, objects with low x-ray attenuation suffered greater variability than objects with high attenuation.^{9,15} Moreover, these CT numbers are markedly influenced by scanner settings.¹¹ Due to these inconsistencies in CT numbers through the CBCT volume, it is not feasible to apply mathematical equations that will accurately derive HU through the CBCT volume. Nevertheless, there is promise to harness the power of CT imaging to decipher more than just morphological information. In a prior clinical study, CBCT gray values assessed at edentulous implant sites showed a trend of decreasing gray values with bone quality type.¹⁴

Current CBCT imaging uses a poly-energetic x-ray beam, with peak energies typically in the range of 90kVp to 110kVp. Attenuation of the x-ray photons is a function of the absorber's atomic number and the energy of the incident photons, and the resultant gray value in an image pixel represents the magnitude of this attenuation. As described above, factors include scatter radiation and reconstruction algorithms impact the accuracy of the true attenuation. In DE-CBCT, attenuation data is assessed using two x-ray sources with different energy spectra. Following acquisition at both energies, mathematical algorithms are applied to compare attenuation between the two energies, and to translate this information into better estimates of bone mineral density. Thus, DE-CBCT provides an approach to assess both morphology and the chemical composition of bone. The proposed study will examine a new CT device, a DE-CBCT unit to provide additional valuable information on bone density, a factor that impacts surgical technique and successful osseointegration.

Practical Applications of BD assessment in dental implant treatment planning: CBCT imaging is widely used to evaluate edentulous sites for potential dental implant placement. Assessment of bone quantity and quality at the potential implant site is an essential objective of imaging. Bone quantity refers to the height and width of the residual alveolar bone. Bone quality represents the thickness of cortical bone, the abundance of trabecular bone, and the overall degree of mineralization.¹⁴ In particular, local quality of bone is a key factor that influences successful osseointegration. The Lekholm and Zarb classification¹⁶ is widely used to categorize bone quantity and quality for implant placement. This classification scheme continues to be used in clinical practice and is recorded as the subjective perception during drilling prior to implant placement. In this classification bone quality is categorized into four types:

Type I: Predominantly cortical bone

Type II: Central core of dense trabecular bone surrounded by a thick layer of cortical bone

Type III: A thin layer of cortical bone surrounding dense trabecular bone

Type IV: A thin layer of cortical bone that surrounds low density trabecular bone

Another widely used assessment, the Misch classification scheme, attempts to categorize subjective radiologic appearance based on a range of HU.¹⁷ Similar to the Lekholm and Zarb classification, this scheme is a subjective assessment, and this limits the depth of practical application for reliable prediction of successful osseointegration.

Misch classification of bone density.

TABLE 15.2 Misch Classification of Bone Density

Classification Type	Radiographic Appearance	Typical Anatomic Location	MDCT Density Range (HU)
D1	Primarily composed of dense cortical bone Marrow spaces are hardly visible	Occasionally in anterior mandible Rarely in posterior mandible	>1250
D2	Thick outer layer of porous cortical bone Coarse trabecular bone pattern	Commonly in anterior and posterior mandible Occasionally in anterior maxilla	850–1250
D3	Thinner layer of porous cortical bone Fine trabecular bone pattern	Commonly in anterior maxilla, posterior maxilla, and posterior mandible Occasionally in anterior mandible	350–850
D4	Faint to imperceptible outline of thin cortical bone Alveolar process is primarily composed of fine trabecular bone	Commonly in posterior maxilla Rarely in anterior maxilla	150–350

HU, Hounsfield units; MDCT, multidetector computed tomography.

Modified from Misch CE. *Contemporary Implant Dentistry*. 3rd ed. St. Louis: Mosby; 2008.

Pre-surgical assessment of bone quality is of high practical relevance. Success rates of implants placed in implants placed in D4 have lower success rates. Modifications to surgical techniques have been devised to improve osseointegration of implants placed in low density bone.¹⁸ In this study, jaw bone density assessed by DE-CBCT will be compared with that measured on MDCT, which is the gold standard for measuring bone density. The ability of DE-CBCT to provide information on jaw bone density could have tremendous impact on case selection and positively impact outcomes.

2.3 Risk-Benefit Assessment

2.3.1 Known potential risks

The risks from this study are related to radiation exposure. Subjects in this study will receive two x-ray examinations:

- MDCT, Maxillofacial, without contrast, Standard treatment, CPT 70486:* The MDCT exam is acquired as standard treatment protocol for dental treatment planning. The typical dose (Dose-area product, DAP) for CT examination of head is 35,000-48,000 mGy•cm².²⁰
- DE-CBCT, Investigational device:* The radiation dose (DAP) is approximately 883 mGy•cm². Overall, the doses from DE-CBCT are low to negligible. Compared with MDCT, the radiation dose from DE-CBCT is approximately one fiftieth (2%).

The radiation doses are orders of magnitude below threshold doses needed to cause deterministic effects. Thus, we do not expect any immediate risks from radiation exposure.

The only potential risks of this added radiation are long-term risk of radiation induced cancer. As described above, the radiation doses delivered by the DE-CBCT device are several-fold lower than diagnostic CT scans, indicating that these risks are much lower than risks of current diagnostic imaging procedures.

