3 OBJECTIVES AND ENDPOINTS

3.1 Primary objective

To evaluate the effectiveness and safety of DE-CBCT to assess jaw bone density and compare these values with MDCT, an established standard for assessment of BD.

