 - HA Concentration (mg/cm³): 0, 100, 200, 400, 600, 800, 1000, 1200
 - Calibration protocol: ISO 9001 QM-System
5. Following the calibration, the research staff will acquire a DE-CBCT imaging. Either mandible or maxilla, depending on the tooth number (imaging site), will be imaged. The appropriate imaging mode will be selected depending on patient size and field of view, and the tube energy set at 60 kV / 90 kV. The DE-CBCT will be acquired with the imaging stent in place.
6. Subject will be scheduled for MDCT scan (Visit 2). The next visit must be within 30days after the visit
 1. Depending on the availability of scheduling on MDCT unit, Visit 2 may occur on the same day as Visit 1.
7. Before the patient returns home, the study staff will educate the subject to contact him/her if adverse events such as nausea, vomiting, hair loss, and oral inflammation occur.

Study Procedure: MDCT scan (Visit 2)

1. Patients scheduled for their MDCT imaging procedures will be confirmed by the imaging facility via the name and date of birth and assigned screening number.
2. For women in childbearing age, pregnancy status will be re-confirmed and recorded.
3. The region of interest (example: tooth number, potential implant site) that requires radiographic imaging will be recorded. The imaging site for MDCT scan will be identical to the one for DE-CBCT scan.
4. The patient will be imaged using the standard clinical protocol for MDCT, and simultaneous scanning of the calibration phantom (QRM-BDC/6).

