8.4 Adverse events and serious adverse events

8.4.1 Definition of adverse event

An Adverse Event (AE) in this clinical trial includes any unfavorable and unintended signs, or symptoms associated with the use of DE-CBCT and CBCT, whether or not considered intervention related. AE may be expected (ex: symptoms related to deterministic radiation effects) or unexpected. Unexpected AE is a sign or symptom not identified in nature, severity, or frequency in the current Investigator's Brochure or of greater severity than expected based on the information in the Investigator's Brochure.

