8.4.3 Classification of an adverse event

Severity of event

- **Mild** – Events require minimal or no treatment and do not interfere with the participant's daily activities.
- **Moderate** – Events result in a low level of inconvenience or concern with the therapeutic measures. Moderate events may cause some interference with functioning.
- **Severe** – Events interrupt a participant's usual daily activity and may require systemic drug therapy or other treatment. Severe events are usually potentially life-threatening or incapacitating. Of note, the term "severe" does not necessarily equate to "serious".

Relationship to study intervention

All adverse events (AEs) must have their relationship to study intervention assessed by the clinician who examines and evaluates the participant based on temporal relationship and his/her clinical judgment. The degree of certainty about causality will be graded using the categories below. In a clinical trial, the study product must always be suspect.

Related – The AE is known to occur with the study intervention, there is a reasonable possibility that the study intervention caused the AE, or there is a temporal relationship between the study intervention and event. Reasonable possibility means that there is evidence to suggest a causal relationship between the study intervention and the AE.

Not Related – There is not a reasonable possibility that the administration of the study intervention caused the event, there is no temporal relationship between the study intervention and event onset, or an alternate etiology has been established.

Expectedness

The Principal investigator in collaboration with the co-Investigators will be responsible for determining whether an adverse event (AE) is expected or unexpected. An AE will be considered unexpected if the nature, severity, or frequency of the event is not consistent with the risk information previously described for the study intervention.

The occurrence of an adverse event (AE) or serious adverse event (SAE) may come to the attention of study personnel during study visits and interviews of a study participant presenting for medical care, or upon review by a study monitor.

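### Safety is in the primary objective, but AE counts in 24 subjects over weeks only weakly bound acute events and cannot address the long-term risk that section 2.3.1 names

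*Combined protocol and SAP*

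**What the plan says.** **Objective and measure.** Section 3.1 states the primary objective as "To evaluate the effectiveness and safety of DE-CBCT to assess jaw bone density", in comparison with MDCT. The Synopsis gives AE incidence as the only safety evaluation. Section 9 repeats the safety aim but plans only Pearson correlation, Bland-Altman plots and Kappa, on a per-protocol set that requires both scans. It gives no AE summary, safety population or safety criterion.

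**Risk.** Section 2.3.1 says "Thus, we do not expect any immediate risks from radiation exposure", and then: "The only potential risks of this added radiation are long-term risk of radiation induced cancer". Section 8.3 likewise anticipates no deterministic effects and will document their absence after each examination. Acute effects do appear elsewhere. Section 8.1 tells subjects to make contact "if adverse events such as nausea, vomiting, hair loss, and oral inflammation occur", and section 8.4.1 says "AE may be expected (ex: symptoms related to deterministic radiation effects) or unexpected".

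**Exposure and time.** Section 4.1 gives every subject both scans. Section 1.2 adds: "Depending on availability of scheduling on MDCT unit, Visit 2 may occur on the same day as Visit 1". The Synopsis says "Subjects will be on study for up to 30 days" and documents AEs on visit days. Section 8.4.4 instead collects events from consent until 7 days (non-serious) or 30 days (serious) after last participation, with onset times and an AE query at each visit.

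**Causality.** Under section 8.4.3 an event can be Related if it is known to occur with the intervention, if there is a reasonable possibility of causation, "or there is a temporal relationship between the study intervention and event". It can be Not Related if, among other grounds, another cause is established.

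**Dose.** Section 2.3.1 gives about 883 mGy·cm² for DE-CBCT and a typical 35,000–48,000 mGy·cm² for head CT. Neither the Synopsis list of CRF assessments nor the schedule in section 1.3 includes dose per scan.

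**The concern.** The planned safety measure does not match the risk that the protocol takes most seriously. AE incidence over weeks can register acute effects, which the protocol expects not to occur. It cannot register a long-term cancer risk. What does bear on that risk is the dose delivered, and the trial is not set up to record it.

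The design also places a second and much larger exposure in every subject, sometimes on the same day. An event that follows both scans carries little information about DE-CBCT alone.

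What is at stake is the conclusion. If the plan is followed exactly and no events occur, the report could present a primary safety objective as met when the data support only a loose limit on acute events. The dose comparison behind the risk-benefit case in sections 2.3.1 and 2.3.3 would stay unchecked in the trial's own subjects.

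**Working it through.** **1. The plan's own figures reproduce.**
- Dose fraction (section 2.3.1): 883/48,000 = 1.84% and 883/35,000 = 2.52%. This agrees with the stated figure of about 2%.
- Sample size (section 5.1): ((1.960 + 0.842)/1.422)² + 3 = 6.88, rounded up to 7. Then 7 × 3 = 21, and 21 × 1.1 = 23.1, rounded up to 24. This sizes a test of zero correlation against 0.89. Safety does not enter the calculation.

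**2. Relative exposure.** 35,000/883 = 39.6 and 48,000/883 = 54.4, so the typical MDCT dose-area product is about 40 to 54 times the DE-CBCT figure.

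**3. What zero events would show.** With n subjects and no events, the exact upper limit on the true rate is 1 − a^(1/n), with a = 0.05 (one-sided 95%) or a = 0.025 (two-sided 95%).

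| n | One-sided 95% | Two-sided 95% |
|---|---|---|
| 24 enrolled | 11.7% | 14.2% |
| 21 evaluable | 13.3% | 16.1% |

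**4. Chance of seeing at least one event in 24**, from 1 − (1 − p)^24:

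| True acute event rate p | Chance of at least one event |
|---|---|
| 0.1% | 2.4% |
| 1% | 21% |
| 5% | 71% |
| 10% | 92% |

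**5. Follow-up.** Taking 30 days on study, section 8.4.4 reaches 30 + 7 = 37 days for non-serious AEs and 30 + 30 = 60 days for serious ones. The Synopsis covers visit days only. None of these windows can show long-term cancer. The documents give no excess risk per scan. For illustration only, an assumed lifetime excess of 1 in 1,000,000 to 1 in 10,000 gives 24 × 0.000001 = 0.000024 to 24 × 0.0001 = 0.0024 expected cases over a lifetime.

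**6. Attribution.**
- *Scans on different days:* onset times and the query at each visit (section 8.4.4) separate events before the second scan from later ones.
- *Scans on the same day:* no AE check is specifically timed between the scans, although section 8.3 documents the absence of deterministic effects after each examination.
- *Events after both scans:* neither arrangement resolves the cause. Under section 8.4.3 the same event can meet Related through timing and Not Related through another cause.
- *Analysis set:* if the per-protocol set in section 9 also governs AEs, a subject scanned only with DE-CBCT, the one case free of MDCT exposure throughout, is left out.

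**The case against.** The strongest reply is that the AE measure is aimed at acute effects and the cancer risk is handled separately, by a dose argument. Sections 8.1, 8.3 and 8.4.1 all concern acute or deterministic effects, and weeks of follow-up are relevant to those. No section says that AE counts will settle the cancer question, and no safety hypothesis or success criterion is set. That is fair. It stops short of an answer, because safety remains part of the primary objective without any statement of this limit, and the dose argument rests on typical figures.

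Several stronger readings are tempting, and the documents do not support them:

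- *Cancer is the only risk named anywhere in the protocol.* That is true of section 2.3.1 only. Acute effects are named in sections 8.1 and 8.4.1.
- *Every event after both scans must be charged to DE-CBCT.* Section 8.4.3 also calls for clinical judgement and lets another cause make an event Not Related. The wording is loose and overlapping, but it compels neither answer.
- *AE counts show nothing.* They give a weak bound on acute events, and separate-day scans allow partial attribution.
- *The MDCT is an added study risk 40 to 54 times larger.* The MDCT is described as standard of care. It complicates attribution. The figure is a typical head-CT dose-area product, not a dose measured here, and a ratio of dose-area products is not a ratio of cancer risks.
- *The 4–17 mA range in section 6.2.2 shows how much dose varies between subjects.* It is a hardware range, capped at 1.12 kW. At 90 kV the maximum is 1,120/90 = 12.4 mA. The better ground for recording dose is section 8.1, where imaging mode depends on patient size and field of view.

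**Conclusion.** The point stands in limited form. As planned, the trial can describe acute AEs and bound their rate loosely: with no events in 24, rates below about 12% (one-sided) or 14% (two-sided) are not excluded. It cannot address the long-term risk named in section 2.3.1, and it does not record the per-scan dose that bears on it. Events after both scans cannot be cleanly attributed, and the partial attribution possible with separate-day scans is not planned.

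A reader might infer that the plan declares DE-CBCT safe if no events occur. It does not say so. The weakness is that nothing in the plan prevents that conclusion.

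The bounds assume that AEs are ascertained in all 24 subjects (21 in the second row of the table). The exposure ratio assumes that the typical head-CT figure is a fair guide to the scans used here. The change is worth making because it is cheap and alters what the trial can claim on its own primary objective.

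**What to change.** 1. **Objective and conclusion.** Limit the safety part of section 3.1, and the conclusion drawn from it, to a description of acute AEs with an exact confidence interval, plus delivered dose.
2. **Dose.** Record on the CRF the dose output that each scanner reports for each DE-CBCT and MDCT scan, and summarise it descriptively. A dose ratio should not become a formal endpoint, since no acceptance criterion exists for it.
3. **AE timing and tabulation.** On same-day visits, record AE status between the two scans. In section 9, tabulate AEs for all scanned subjects, not only the per-protocol set, as after DE-CBCT only, after MDCT only, or after both.
4. **Reconcile the text.** Use one AE window in place of the visit-day rule in the Synopsis and the 7-day and 30-day rules in section 8.4.4. Remove the overlap between Related and Not Related in section 8.4.3.

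The cost is a few CRF fields, one AE check on same-day visits, and wording changes, with no added subject or visit. The downside is a narrower safety claim. Item 2 assumes that both scanners report a dose figure. The MDCT model is not yet specified in section 6.2.1, so this should be confirmed. If the units differ, report each in its own unit.
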